13. STATISTICAL CONSIDERATIONS

13.1 Study Design/Endpoints

The proposed study is an open-label, randomized phase 2 multicenter trial evaluating cobimetinib in combination with atezolizumab compared with atezolizumab monotherapy in unresectable cholangiocarcinoma.

The primary clinical endpoint is progression free survival and the primary objective of the trial is to determine whether the combination of cobimetinib in combination with atezolizumab yields a clinically compelling antitumor activity measured as progression free survival (PFS). Additional secondary endpoints include safety, objective response rate (ORR, assessed by RECIST 1.1), overall survival (OS), and other immunologic correlates.

The principle correlative objective of the trial is to determine whether the combination of cobimetinib and atezolizumab increases immune response compared to atezolizumab monotherapy. The change CD8+ density within tumor after 21 days of treatment, as compared to baseline, is an integrated biomarker for this clinical trial.

The study is planned with 76 evaluable subjects (38 subjects per treatment arm), to achieve 90% power using a 1-sided test with alpha=0.05. Both of these drugs are in common use and will be given at full dose. The combination of cobimetinib and atezolizumab was previously tested, and well tolerated in a similar population of patients with metastatic colorectal cancer, so unacceptable rates of toxicity are not expected, but the present study will be continuously monitored for adverse events. The primary study team made up of the study PI [name], [REDACTED] Dr. [REDACTED], and lead study nurse and coordinator at the lead site Johns Hopkins will meet weekly to discuss adverse events. In addition, the primary study team will have bimonthly calls with representatives at all the enrolling sites to monitor toxicity continuously.

Progression-free survival is defined as the duration of time from date of randomization to time of progression or death. The evaluable population includes all subjects who have completed at least one dose of therapy and have received at least one follow-up scan. Patients who come off of study treatment for clinical progression prior to the first follow-up scan (i.e. clinical progression)

will also be considered evaluable and will be coded as progressors for the analysis. Due to the rapid progression of the disease in the majority of patients, little loss to follow up is expected, but subjects who are lost to follow-up as of the data analysis cutoff date will be right-censored. The censoring date will be determined from the date the subject was last evaluated for progression. PFS within each treatment arm will be summarized descriptively using Kaplan-Meier plots, and compared between groups, under the assumption of Cox proportional hazards, using the stratified log-rank test to account for tumor site. An interim analysis will be conducted when half the required PFS events have been observed (35). The trial will be stopped early for futility if the p-value from the log-rank statistic is greater than 0.5 (i.e., the PFS is worse for study arm B than for study arm A).

The analysis will be stratified on site of disease (gallbladder cancer, intrahepatic cholangiocarcinoma, and extrahepatic cholangiocarcinoma). An interim analysis will be conducted when half the required PFS events have been seen (35), and the trial will be stopped early for futility if median PFS is lower by any amount, under the combination therapy than under monotherapy.

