4.4 General Guidelines

Following registration, patients should begin protocol treatment within 7 days. Issues that would cause treatment delays should be discussed with the Principal Investigator. If a patient does not receive protocol therapy following registration, the patient's registration on the study may be canceled. The Study Coordinator should be notified of cancellations as soon as possible.

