5.4 Duration of Follow Up

All subjects should continue to be monitored for disease status at least every three months until death, withdrawal of consent, or study closure, whichever occurs first. Patients removed from study for unacceptable adverse event(s) will be followed until resolution or stabilization of the adverse event.

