J: Baseline scans must be done < 4 weeks prior to randomization. Tumor measurement will be performed with contrast CT chest/abdomen/pelvis. Non-contrast CT chest/abdomen/pelvis or CT Chest and MRI Abdomen/pelvis will be performed in subjects with contraindications or intolerance to contrast dye. Imaging will be repeated every 8 weeks (+/- 4 days), irrespective of dosing schedule or treatment delays. For patients continuing treatment past progression, the subsequent scan should be performed 6-8 weeks following the initial scan demonstrating progression (see section 5.3.1.). If this repeat scan does not show further progression, imaging frequency can revert to every 8 weeks (+/- 4 days).

K: Only for subjects with tumor that in the opinion of the study treatment team is safely accessible for biopsy.

L: Baseline research blood collection will be collected prior to dosing of any study therapy (visit window day -7 to 0, prior to dosing). Additional on-treatment research bloods will be collected on cycle 1 day 15 (day -4 to 0), on cycle 2 day 1 (day -4 to 0), and at the time of progression (+/- 7 days). No research blood is needed for day 1 of any cycle beyond cycle 2. Research blood samples should be collected and shipped on Monday-Thursday only to avoid problems with weekend/holiday delivery. For additional details, see section 9.3.1.

M: For patients randomized to cobimetinib plus atezolizumab (*study arm B only*).

N: Off-study evaluations will be completed 4 weeks after meeting at least one of the criteria listed in section 5.3.

O: Patients receiving cobimetinib (*study arm B only*).

P: Adverse events will be assessed at least 90 days after the last dose of either study agent. For patients removed due to unacceptable toxicity, they will be followed until resolution of the adverse event.

Q: Scans do not need to be repeated if a scan has been performed within 8 weeks.

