11.1.6 Progression-Free Survival (PFS)

PFS is defined as the duration of time from date of randomization to time of progression or death, whichever occurs first.

Note: For participants who receive treatment beyond disease progression (as described in 5.3.1), PFS will be dated as follows.

- For patients who have progressive disease on two sequential scans, the date of progression will be backdated to the time of first progression.
- For patients who do not have progressive disease on the scan after progressive disease was first documented, the date of progression will be dated to the time that a second scan shows progression.

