11.1.7 Overall Survival (OS)

OS is defined as the duration of time from date of randomization to time of death.

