13.4 Analysis of Secondary Endpoints

Overall survival is defined as the duration of time from date of randomization to time of death. Subjects lost to follow-up or whose vital status is unknown, will be right-censored at the date the subject was last known to be alive. Every effort will be made to determine outcome, including phone calls, certified mail, and the checking of public records as necessary. The evaluable population is as defined for the primary endpoint. Results will be summarized descriptively using Kaplan-Meier plots, and compared between groups, under the assumption of proportional hazards, using the stratified log-rank test to account for tumor site.

The density of CD8+ T cells in each treatment group, at baseline and after treatment, will be visualized using boxplots, and described using summary statistics including means and s.d. presented with 95% confidence intervals. A student t-test or nonparametric Wilcoxon rank-sum test will be used to determine whether the increase in CD8+ T cells is greater in treatment arm B (combination cobimetinib plus atezolizumab) than in treatment arm A (atezolizumab monotherapy).

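### PFS and OS are compared in a set that requires a dose and a follow-up scan, so some randomised patients, including some who die before the first scan, drop out of both comparisons

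*Combined protocol and SAP*

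**What the plan says.** Section 13.1 defines the efficacy set: "The evaluable population includes all subjects who have completed at least one dose of therapy and have received at least one follow-up scan". It makes one exception. Patients who leave treatment for clinical progression before the first follow-up scan "will also be considered evaluable and will be coded as progressors for the analysis". Section 13.4 says of OS: "The evaluable population is as defined for the primary endpoint". Neither section, nor any other, specifies a PFS or OS analysis of all randomised patients.

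Both endpoints start at randomisation and count death. Section 11.1.6: "PFS is defined as the duration of time from date of randomization to time of progression or death, whichever occurs first". Section 11.1.7: "OS is defined as the duration of time from date of randomization to time of death". The first follow-up scan is due at 8 weeks (section 11.1).

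Follow-up does not end with treatment. Section 5.4: "All subjects should continue to be monitored for disease status at least every three months until death", or until withdrawal of consent or study closure. Note J of the study calendar schedules imaging "irrespective of dosing schedule or treatment delays". Section 4.4 covers patients who never start: "If a patient does not receive protocol therapy following registration", the registration may be cancelled.

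Section 13.2 plans about 82 patients to obtain at least 76 evaluable.

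**The concern.** Membership of the set depends on what happens after randomisation. Three groups fall outside it:

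1. dosed patients who die before the first scan without first coming off treatment for clinical progression;
2. dosed patients who stop early and are never rescanned;
3. patients never dosed.

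Stopping treatment does not in itself exclude anyone; never being rescanned does.

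Group 1 matters most, because each such patient has an event on both endpoints and the rule deletes it. Such deaths are foreseeable: section 13.5.2 lists early death from malignant disease, from toxicity and from other causes as response categories, and section 3.1.5 asks only for a life expectancy above 2 months, close to the 8-week scan. For OS the scan requirement has no rationale, and it also discards known survival time of living patients.

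The trial is open-label and Arm B adds a second drug, so early loss could differ by arm. For a patient with no scan, the investigator's label for an early stop decides between an event (clinical progression) and exclusion (for example, toxicity). If exclusions relate to outcome and are unequal between arms, the log-rank comparison is biased, in a direction the documents do not determine. The deaths still appear in safety reporting, so the problem is confined to the efficacy comparisons.

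**Working it through.** **1. The plan's own figure.** Inputs from sections 13.1 and 13.2: medians 2 and 4 months (HR 0.5 if exponential), 1:1 allocation, one-sided alpha 0.05, power 90%, 71 events among 76 patients.

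- Schoenfeld events = 4(1.645 + 1.282)² / (ln 2)² = 71.3.
- Power at 71 events = Φ(√71 × 0.693/2 − 1.645) = Φ(1.275) = 89.9%.

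The stated design reproduces. The sample size is not in error.

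**2. Who counts.** The rule set against the endpoint definitions:

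| Patient with no follow-up scan | In the set? | Under the endpoint definitions |
|---|---|---|
| Off treatment for clinical progression | Yes, as event | Event |
| Dies, not first taken off for clinical progression | No | PFS and OS event |
| Alive, never rescanned | No | PFS: censored near time zero; OS: known follow-up |
| Never dosed | No | Follow-up from randomisation |

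For PFS the damage therefore comes mainly from the second row. For OS the later rows also lose information.

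**3. Illustration for PFS.** Assumption: the 82 − 76 = 6 patients are all PFS events before week 8 (56/30.4375 = 1.84 months). The documents do not say what they are. Simulation: 41 per arm, exponential times, 12 months' follow-up, randomly chosen pre-week-8 events deleted, unstratified one-sided log-rank at 1.645, 40,000 runs per scenario. The medians are the plan's 2 months and the upper end of the 2-3 months in section 2.1. True HR is 1.

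| Early events deleted, A/B | Type I error, median 2 | Type I error, median 3 |
|---|---|---|
| 0/0 | 5.4% | 5.1% |
| 6 unrelated to outcome | 5.3% | 5.1% |
| 3/3 | 5.7% | 5.5% |
| 0/2 | 7.6% | 7.6% |
| 2/0 | 3.8% | 3.8% |
| 2/4 | 7.9% | 8.5% |
| 1/5 | 10.4% | 11.6% |
| 0/6 | 13.9% | 16.1% |
| 4/2 | 4.0% | 3.9% |
| 5/1 | 2.8% | 2.6% |
| 6/0 | 1.8% | 1.6% |

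With 0/6 the apparent HR is 0.86-0.88; with 6/0 it is 1.13-1.16. A separate run without censoring (20,000 runs) agrees: 14.1% and 15.5% for 0/6, 1.8% and 1.7% for 6/0.

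Power at 2 versus 4 months: all 82 patients 91.5%; 3/3 92.3%; 0/6 97.6%; 6/0 79.1%.

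**4. Average over splits.** If each of the six lost events is equally likely to fall in either arm, the splits have weights 1, 6, 15, 20, 15, 6, 1 out of 64. For median 2: (13.9 + 6×10.4 + 15×7.9 + 20×5.7 + 15×4.0 + 6×2.8 + 1.8)/64 = 6.1%. For median 3 the same sum gives 6.2%.

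**5. Illustration for OS.** The documents give no OS median, so 4 to 10 months is assumed. With no true difference, deleting two early deaths from Arm B alone gives 7.9-9.1%; two from Arm A alone gives 3.1-3.5%.

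**6. Power if all randomised patients are analysed.** At the plan's event fraction, 82 × 71/76 = 76.6 events, and power = Φ(√76.6 × 0.693/2 − 1.645) = 91.8%. If the extra six contribute no events, power stays at 89.9%.

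**The case against.** The strongest reply concerns size. The clinical-progression clause already keeps the likeliest early failures. Entry requires ECOG 0-1 and a life expectancy above 2 months, so unscanned deaths without that label may be few. The six patients between 82 and 76 could equally be never dosed or withdrawn, with almost no effect on PFS. The 14-16% figure is conditional on an extreme split (probability 1 in 64 if arm is random); averaged over splits the error is about 6%. All of this stands as context. It shows that material distortion needs losses related to both outcome and arm. It does not show that such losses are absent, and an open-label add-on design gives no assurance of it.

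Second, the calendar plans tumour measurement at the off-study visit, and section 11.1.4.3 asks for objective progression to be documented after discontinuation, so fewer patients go unscanned. That narrows group 2. It does nothing for patients who die, and note Q waives the scan if one was done within 8 weeks, which read literally could be the baseline scan.

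Third, no sentence says outright that the PFS log-rank test is run in the evaluable set. True, but the definition sits in the PFS analysis text, the trial is sized on 76 evaluable patients, and section 13.4 calls it the population of the primary endpoint. For OS the link is explicit.

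**Conclusion.** The concern holds: this is a stated rule that gives a wrong result, not a missing detail. As written, some randomised patients with a PFS and an OS event are removed from two comparisons that are defined from randomisation and count death.

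The size cannot be derived from the documents. Within the plan's own allowance of six, and assuming those six are early events, the one-sided type I error ranges from about 2% to 16% according to the arms they fall in; it is about 6% if they fall at random and unchanged if exclusion is unrelated to outcome. An imbalance of only two events moves it to about 8% or 4%. These figures rest on exponential times and an unstratified test. The point concerns the primary comparison and must be fixed.

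A separate, smaller inconsistency is that response has three conflicting evaluable populations: all dosed patients and the primary-endpoint evaluable set (both in section 13.5.2), and patients with at least one cycle and a re-evaluation, or early objective progression (section 11.1.1).

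**What to change.** - Make the primary PFS and OS analyses all randomised patients by assigned arm, including any never dosed.
- Count every death as an event, including deaths before the first scan. Keep the rule that codes clinical progressors as events.
- For PFS, censor living patients with no post-baseline assessment at randomisation. This is numerically the same as leaving them out of the log-rank test, but it keeps them accounted for. For OS, censor at the date last known alive.
- Keep the evaluable set as a supportive PFS analysis, with the number and reason for exclusion reported by arm. Remove it for OS.
- State which set feeds the 35-event futility analysis.
- Use one response denominator in sections 11.1.1 and 13.5.2, for example all treated patients with early deaths and not-assessable patients as non-responders.

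The cost is protocol and SAP wording: section 5.4 already requires follow-up of all subjects, and power is not reduced. PFS and ORR may look slightly less favourable. Because this version is dated October 2022 and section 12.1 gives the principal investigator and statistician access to the data at all times, the amendment should record that the change was made on design grounds, without reference to outcomes by arm.

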12.1 Study Oversight

This protocol is monitored at several levels, as described in this section. The Study Principal Investigator is responsible for monitoring the conduct and progress of the clinical trial, including the ongoing review of accrual, patient-specific clinical and laboratory data, and routine and serious adverse events; reporting of expedited adverse events; and accumulation of reported adverse events from other trials testing the same drug(s). The Study Principal Investigator and statistician have access to the data at all times through the CTMS web-based reporting portal.

The Study Principal Investigator will have, at a minimum, quarterly conference calls with the site Investigators, study collaborators, and the CTEP Medical Officer(s) to review accrual, progress, and pharmacovigilance.

All Site Principal Investigators who register/enroll patients on a given protocol are responsible for timely submission of data via Medidata Rave and timely reporting of adverse events for that particular study. This includes timely review of data collected on the electronic CRFs submitted via Medidata Rave.

All studies are also reviewed in accordance with the enrolling institution's data safety monitoring plan.

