13.2 Sample Size/Accrual Rate

Approximately 82 patients with unresectable cholangiocarcinoma will be enrolled in this randomized phase 2 trial with the goal of accruing at least 76 evaluable subjects, with progression free survival (PFS) as the primary endpoint. We plan to enroll approximately 6 patients per month across the multiple trial sites, and because of the rapid progression of the disease, expect little or no censoring. We anticipate fully enrolling this trial within 18 months, permitting an average of 12 months of follow up, and completing the study within 3 years. This design yields 90% power at a one-sided type I error rate of 5% assuming a difference in median PFS between the arms of 2 months (2 months vs. 4 months), and assuming that 71 events will have occurred among 76 patients over the study period. Calculations were performed without stratification, as it is not known whether outcome varies by site.

Patients with tumor that is safely accessible for biopsy will obtain a biopsy at study baseline and a repeat on-treatment biopsy at treatment day 21. Based on previous clinical experience, we anticipate that paired biopsy samples will be successfully obtained in at least 50% of participants. We anticipate obtaining approximately 20 subjects in each treatment arm with paired samples available for analysis, offering 80% power for detecting an increase in CD8+ density equal to 0.8s.d., using a one-sided t-test with alpha=0.05, and more than 90% power for detecting an effect size of 1.0s.d.

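### Section 13.1 gives two different futility rules for the same 35-event interim and does not say which one governs

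*Combined protocol and SAP*

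**What the plan says.** Section 13.1 of the combined protocol and SAP sets out the interim look in two consecutive paragraphs. Both place it at half the required PFS events (35).

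- First paragraph: "The trial will be stopped early for futility if the p-value from the log-rank statistic is greater than 0.5". A bracketed gloss explains this as a poorer PFS result on Arm B than on Arm A.
- Second paragraph: "the trial will be stopped early for futility if median PFS is lower by any amount, under the combination therapy than under monotherapy".

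Neither paragraph refers to the other. The interim sentences do not state the sidedness of the p-value or whether the interim test is stratified. The primary comparison is made "using the stratified log-rank test to account for tumor site", and the design is sized "to achieve 90% power using a 1-sided test with alpha=0.05". No other section mentions futility.

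**The concern.** The two sentences name different statistics. The stratified log-rank statistic accumulates evidence over the whole curve within each tumor-site stratum. The median rule compares one point on each arm's curve. With only 35 events across two arms, the sign of the first and the order of the second can differ.

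When they differ, the protocol gives no answer. Taken literally, two sentences that each say the trial will be stopped mean that either one suffices. A team could equally hold that both must be met, or that only one was intended. A pre-specified stopping rule is meant to fix the decision before the data are seen, and this one does not. The trial is open-label, and Section 12.1 states: "The Study Principal Investigator and statistician have access to the data at all times through the CTMS web-based reporting portal". Section 12.4 mentions a data monitoring committee only conditionally. The reading could therefore be settled after both results are known.

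**Working it through.** **Design figures.** Inputs from Sections 13.1 and 13.2: 76 evaluable patients, 38 per arm; about 6 patients per month; medians of 2 versus 4 months (HR 0.5 if PFS is exponential); one-sided alpha 0.05; 90% power; 71 events.

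- Schoenfeld events: (1.645 + 1.282)² / (0.25 × (ln 0.5)²) = 71.3, against 71 in the plan.
- Power at 71 events: Φ(0.693 × √(71/4) − 1.645) = Φ(1.275) = 89.9%, against 90%.
- Half of 71 is 35.5, against 35.

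The plan's figures reproduce.

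**Log-rank rule, normal approximation.** At 35 events the mean of Z under HR 0.5 is 0.693 × √(35/4) = 2.05.

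- One-sided p > 0.5 means Z < 0. The probability is 50% at HR 1 and Φ(−2.05) = 2.0% at HR 0.5.
- Two-sided p > 0.5 would mean |Z| < 0.674. At HR 0.5 the probability is Φ(−1.376) − Φ(−2.725) = 8.1%, and it would include trials favoring Arm B. The gloss therefore fits only a one-sided p.

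**Simulation of both rules.** Interim at the 35th and final analysis at the 71st recorded event. A log-rank stop means the stratified Z favors Arm A. A median stop means the Kaplan-Meier median is lower on B than on A; tied medians, or a B median not reached, do not count as lower. Assumptions not in the documents: exponential PFS, strata shares of 25/50/25% with no stratum effect, and equal medians of 3 and 4 months as extra no-effect cases. Event dates are either continuous or follow Section 10, footnote J ("Imaging will be repeated every 8 weeks (+/- 4 days), irrespective of dosing schedule or treatment delays"), with an assumed 0, 20 or 40% of events dated off the scan schedule. There were 20,000 trials per cell (standard error about 0.3 points).

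| % of trials | Continuous | ±4-day scans | + 20% off-schedule | + 40% off-schedule |
|---|---|---|---|---|
| Rules conflict, 2 v 2 months | 20.8 | 22.3 | 22.3 | 22.2 |
| Rules conflict, 3 v 3 | 20.1 | 21.2 | 21.1 | 20.6 |
| Rules conflict, 4 v 4 | 18.7 | 19.7 | 20.1 | 20.2 |
| Rules conflict, 2 v 4 | 4.4 | 4.7 | 5.2 | 5.2 |
| Stop at 2 v 2: both required | 39.6 | 36.3 | 36.9 | 37.7 |
| Stop at 2 v 2: log-rank only | 49.8 | 50.6 | 50.4 | 50.3 |
| Stop at 2 v 2: median only | 50.1 | 44.3 | 45.7 | 47.2 |
| Stop at 2 v 2: either suffices | 60.4 | 58.6 | 59.2 | 59.8 |
| Stop at 2 v 4: both required | 1.9 | 1.9 | 2.2 | 2.2 |
| Stop at 2 v 4: log-rank only | 3.0 | 3.5 | 3.7 | 3.8 |
| Stop at 2 v 4: median only | 5.3 | 5.1 | 5.9 | 5.8 |
| Stop at 2 v 4: either suffices | 6.3 | 6.7 | 7.4 | 7.4 |

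The conflict rate is the either figure minus the both figure: for continuous dates at 2 v 2, 60.4 − 39.6 = 20.8.

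**Sensitivity.** Unstratified testing, other strata shares, Poisson accrual at 6 or 4.6 per month, blocked randomization and unrounded scan dates were also tried. Across all of these, conflict stays at 18.7–22.3% with no effect and 4.3–5.6% at 2 v 4. False stops at 2 v 4 are 1.6–2.4% (both), 2.3–4.0% (log-rank), 5.0–6.5% (median) and 5.9–7.6% (either). Power lost is 0.7–1.2 points (log-rank), 2.3–3.4 (median) and 2.8–3.7 (either). One-sided type I error is 4.5–5.5% on every reading. Simulated stratified power before any futility rule was 84.8–86.6%; these runs measure the cost of the rules and are not offered as a challenge to the 90%.

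**Cross-check.** A separately coded simulation (6,000 trials per cell, continuous dates) gave conflict of 21.2% at 2 v 2 and 4.7% at 2 v 4. Power was 86.5% with no interim, 85.8% under the log-rank rule, 84.1% under the median rule and 83.8% if either suffices.

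**The case against.** The strongest reply is that one rule was meant. The gloss on the log-rank sentence already says, in effect, that PFS looks worse on Arm B. The second sentence may say the same on the scale used to state the design effect. Section 13.1 assumes proportional hazards, under which a true hazard ratio above 1 and a lower true median on Arm B are the same condition. The repeated interim sentence looks like drafting duplication. This is plausible, but the equivalence holds for the true quantities and not for the estimates at 35 events. The decision is made on the estimates.

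Four further points bear on weight.

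- **Near-ties.** With no effect (2 v 2, 3,000 trials per cell), about 94% of conflicting trials had |Z| below 1, with a median |Z| of about 0.33. That stands. However, a rule set at p = 0.5 puts its boundary exactly there.
- **Small inferential cost.** Type I error is not inflated and little power is lost. That also stands. With no effect, neither stopping nor continuing is an inferential error, though continuing costs patients and time.
- **Model dependence.** The median rule's higher false-stop rate reverses if progression falls on an exact 8-week grid: 1.4% against 3.0% for log-rank at 2 v 4. On that grid about half of no-effect trials have tied medians, and conflict is 26–31% with no effect and about 3% at 2 v 4. Footnote J allows ±4 days, so the grid is not used for the main figures. The ordering of the two rules should still be read with that qualification. The conflict between them remains on the grid.
- **Data access.** Section 12.1 is general oversight text, and the access would exist under any rule. That is fair. It shows only that nothing in the plan would settle the reading before the results are known.

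**Conclusion.** The concern holds. Section 13.1 contains two mandatory futility rules for one look, and they can give opposite instructions. Under exponential PFS with continuous or ±4-day scan dates, they conflict in 19–22% of trials with no effect and 4–6% at 2 versus 4 months. The chance of stopping an ineffective combination varies by about 20 points with the reading. The chance of stopping an effective one varies from about 2% to about 7%.

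The harm is not to the type I error, and the power loss is modest on any reading. It lies in a go/no-go decision on the primary endpoint that the plan does not determine. The sizes rest on the assumed exponential PFS, strata shares and event-date models. The contradiction itself rests only on the text.

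**What to change.** Keep one interim rule in Section 13.1 and state its statistic, sidedness and stratification. The log-rank rule is the natural choice because it matches the primary analysis. Suggested wording:

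> At 35 PFS events, the trial will be stopped for futility if the one-sided stratified log-rank p-value (alternative: Arm B better) exceeds 0.5.

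Delete the median-PFS sentence. If the sponsor prefers the median rule, delete the log-rank sentence instead and say how tied medians and medians not yet reached are handled.

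The cost is one sentence removed and a few words added. No extra patients, events or data are needed, and the sample size does not change.
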